# mCRPC patients (Part 1 and Part 2 Arms 1A and 1B)

Bone scintigraphy (bone scans) and CT/MRI chest, abdomen, and pelvis should be performed at the following time points:

- During the screening period (within 28 days before C1D1 [baseline])
- At C3D15 (± 7 days)
- Then every 8 weeks (±7 days) for 24 weeks, i.e., between C6D1 and C8D15
- And every 3 months (±7 days) thereafter, i.e., from C11D15 until disease progression is assessed by the investigator or the start of new anti-cancer therapy or withdrawal of consent, or death, whichever occurs first
- At EoT visit (only if clinically indicated); not required if previous imaging was performed within ≤9 weeks before the EoT visit

Patients in Arm 1B who move to treatment with cemiplimab monotherapy following progression after BNT112 monotherapy, should have radiographic assessments performed every 3 months ( $\pm 7$  days) thereafter, until disease progression is assessed by the investigator or the start of new anti-cancer therapy or withdrawal of consent, or death, whichever occurs first.

CONFIDENTIAL Page 73 of 122

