# Progression-free Survival

PFS is defined as the time from the date of first dose of IMP/randomization to the date of first disease progression, or death from any cause, whichever occurs first. PFS will be analyzed using the Kaplan-Meier method. Patients alive and without disease progression at the data cut-off date or patients lost to follow-up will be censored at the day of their last tumor assessment. If no baseline or post-baseline tumor assessment is available, the patient will be censored at the date of first dose of IMP/randomization. Additional censoring rules will be defined in the SAP.

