response (CR or PR) + 1) / 30.4375 in case of censoring.

DoR based on iRECIST (central reading):

OR is defined as iCR or iPR. Disease progression is defined as tumor response =
Confirmed progressive disease (iCPD)

DoR expressed in months for patients whose objective response was confirmed iCR or
iPR = (MIN [Date of first documented disease progression (iCPD), date of death from any
cause] – Date of first documented overall response (iCR or iPR) + 1) / 30.4375 for events

or

(Date of the last evaluable response assessment – Date of first documented overall
response (iCR or iPR) + 1) / 30.4375 in case of censoring.

Progression-free survival

PFS will be analyzed for Part 1 and Part 2 Arms 1A and 1B, Arm 2 and Arm 3.

PFS is defined as the time from the date of the first dose of IMP to the date of the first
disease progression, or death from any cause, whichever occurs first.

Only death dates reported prior to or at the date of trial discontinuation will be considered
in the PFS analysis.

PFS will be analyzed using the Kaplan-Meier method. Kaplan-Meier plots will be
generated.

Patients alive and without disease progression at the data cut-off date or patients lost to
follow-up will be censored at the day of their last response assessment.

Only response assessments prior to or at the start date of the first subsequent anti-cancer
therapy will be considered for PFS analysis. PD within 14 days after the start date of the
first subsequent anti-cancer therapy will be considered.

If no post-baseline tumor response is available, the patient will be censored at the date of
the first dose of IMP.

PFS expressed in months = (MIN [Date of first disease progression, date of death from
any cause] – date of first dose of IMP + 1) / 30.4375 if the patient has a PFS event

or

(Date of last evaluable response assessment – date of first dose of IMP + 1) / 30.4375 in
case of censoring.

In the case that date of the first dose of IMP is missing, randomization date will be used for the calculation of PFS.

For Part 1 and Part 2 Arms 1A and 1B, PFS will be analyzed separately based on PCWG3 and iRECIST (central reading).

Sensitivity analyses of PFS will be performed using the ITT set and the PP set depending on the number of patients excluded.

Overall survival

OS will be analyzed for Part 1 and Part 2 Arms 1A and 1B, Arm 2 and Arm 3.

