(MIN [Date of first documented disease progression (iCPD) after start of cemiplimab treatment, date of death from any cause] – Date of first documented overall response (iCR or iPR) + 1) / 30.4375 for events

or

(Date of the last evaluable response assessment after start of cemiplimab treatment – Date of first documented overall response (iCR or iPR) + 1) / 30.4375 in case of censoring.

Progression-free survival based on PCWG3 or iRECIST (central reading)

PFS will be analyzed separately for PCWG3 and iRECIST (central reading).

PFS is defined as the time from the date of the first dose of cemiplimab treatment to the date of the first disease progression, or death from any cause, whichever occurs first.

Only death dates reported prior to or at the date of trial discontinuation will be considered in the PFS analysis.

PFS will be analyzed using the Kaplan-Meier method. Kaplan-Meier plots will be generated.

Patients alive and without disease progression after start of cemiplimab treatment at the data cut-off date or patients lost to follow-up will be censored at the day of their last response assessment.

Only response assessments prior to or at the start date of the first subsequent anti-cancer therapy will be considered for PFS analysis. PD within 14 days after the start date of the first subsequent anti-cancer therapy will be considered.

If no post-baseline response assessment after start of cemiplimab treatment is available, the patient will be censored at the date of the first dose of cemiplimab treatment.

PFS expressed in months = (MIN [Date of first disease progression after start of cemiplimab treatment, Date of death from any cause] – date of first dose of cemiplimab treatment + 1) / 30.4375 if the patient has a PFS event

or

(Date of last evaluable response assessment after start of cemiplimab treatment – date of first dose of cemiplimab treatment + 1) / 30.375 in case of censoring.

Progression-free survival 2 (PFS2) based on PCWG3

PFS2 is defined as the time from the date of the first IMP to the date of the first disease progression after start of cemiplimab per PCWG3, or death from any cause, whichever occurs first.

Only death dates reported prior to or at the date of trial discontinuation will be considered in the PFS2 analysis.

PFS2 will be analyzed using the Kaplan-Meier method. Kaplan-Meier plots will be generated.

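### The no-assessment censoring rule for PFS and PFS2 has no exception for death, so it contradicts the endpoint definition and, read literally, drops deaths before the first assessment

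*SAP*

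**What the plan says.** **Definitions.** For the cemiplimab phase, SAP 8.7.4.2 states: "PFS is defined as the time from the date of the first dose of cemiplimab treatment to the date of the first disease progression, or" any-cause death if that comes first. For PFS2: "PFS2 is defined as the time from the date of the first IMP to the date of the first disease progression after start of cemiplimab", again with death as the alternative event. Main PFS in SAP 8.7.4.1 has the same structure, counted from first IMP.

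**No-assessment rule.** Cemiplimab-phase PFS and PFS2 share one sentence: "If no post-baseline response assessment after start of cemiplimab treatment is available, the patient will be censored at the date of the first dose". The dose meant is the first one of cemiplimab. Main PFS in SAP 8.7.4.1 has: "If no post-baseline tumor response is available, the patient will be censored at the date of" first IMP dose. Protocol 9.4.4 has: "If no baseline or post-baseline tumor assessment is available, the patient will be censored at the date of first dose of IMP/randomization".

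**Neighbouring rule.** The general censoring sentence for cemiplimab-phase PFS is restricted: "Patients alive and without disease progression after start of cemiplimab treatment at the data cut-off date or patients lost to follow-up will be censored". The date used is that of the last response assessment.

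**Limit on deaths.** The only stated limit in these SAP paragraphs is that a death counts if it is reported no later than trial discontinuation.

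**Imaging.** After the switch, Protocol 8.1.1.1 says patients "should have radiographic assessments performed every 3 months".

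**The concern.** The two censoring sentences are written differently. The general one covers patients who are alive or lost to follow-up. The no-assessment one covers everybody without an assessment, including patients who died before one could be made. The definition makes such a death an event on its date; the censoring sentence makes it a non-event at first dose. Nothing in either document says which prevails.

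Early deaths are the worst outcomes in the set, so censoring them at the start can only raise the estimated curve. Two programmers working from this SAP could produce different PFS tables and Kaplan-Meier plots.

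**Working it through.** The plan gives no figure that depends on this rule, so there is nothing to reproduce. The check has two parts: whether other text resolves the conflict, and how many deaths are exposed.

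**1. Does the event formula settle it?** No. It reads "PFS expressed in months = (MIN [Date of first disease progression after start of cemiplimab treatment, Date of death from any cause", measured from first cemiplimab, but it is given for patients already classed as having an event. It dates events and does not decide who has one.

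**2. Are the exposed patients in the analysis sets?**
- Cemiplimab-phase PFS and PFS2 use the Cemi Mono on PD set (SAP 7.1), which needs one cemiplimab dose and no later assessment. Early deaths are in it.
- Main PFS uses the mITT set, which already requires a post-baseline clinical or imaging assessment. The rule matters mainly in the ITT sensitivity analysis, listed as optional in SAP 11.1.1. Patients brought back without an assessment would get a time of 1 day (0.03 months) and no event. They would add nothing to the estimate, so the ITT curve would largely repeat the mITT curve.

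**3. How long is the exposed window?** For iRECIST by central reading it runs to the first scan, 3 months. For PCWG3 it depends on what a response assessment is. SAP 8.2 uses the term for PSA and builds PCWG3 response and progression partly from PSA. Protocol 1.5 schedules PSA before dosing at the first cemiplimab cycle and at every later 21-day cycle. If PSA counts, the window is about 21/30.4375 = 0.69 months.

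**4. Size.** With exponential survival and median m months, the share dead by time t is 1 − 2^(−t/m). For scale, also assume progression is exponential with a 4-month median, independent of death, and seen only at the scan. PFS just after a 3-month scan is then 2^(−3/4) = 0.59 if early deaths are censored at first dose, and 0.59 × P(alive at 3 months) if they count.

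| Median survival (months) | Source | Dead by 3 months | Dead by 3 weeks | 3-month PFS, deaths counted | 3-month PFS, literal rule |
|---|---|---|---|---|---|
| 34 | Protocol 2.1.1, mCRPC in general | 5.9% | 1.4% | 0.56 | 0.59 |
| 16 | Protocol 2.1.1, mCRPC in general | 12.2% | 2.9% | 0.52 | 0.59 |
| 12 | assumed | 15.9% | 3.9% | 0.50 | 0.59 |
| 9 | assumed | 20.6% | 5.2% | 0.47 | 0.59 |
| 6 | assumed | 29.3% | 7.7% | 0.42 | 0.59 |

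The last two columns apply to imaging-based PFS. The gap runs from 3.5 points (m = 34) to 17 points (m = 6).

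In small numbers: with an assumed 20 switchers, 2 early deaths and no other event, 3-month PFS is 18/20 = 90% if the deaths count and 100% (18 at risk) if they are censored. With 10 switchers and 2 deaths it is 80% against 100%.

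**5. PFS2.** The clock starts at first IMP and censoring falls at the first cemiplimab dose. The patient keeps the time before the switch, and only the death is lost.

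**The case against.** The best defence is that this is loose drafting with an obvious intended meaning. The definition counts any-cause death and the event formula takes the earlier of progression and death. The disputed sentence follows a rule that censors at the last response assessment, so its natural job is to supply a date when there is none. Where the SAP means to disregard deaths, namely those after trial discontinuation, it says so. A sensible programmer could well count the early death. This stands as far as it goes: the loss of deaths is a literal reading and not a certainty. It does not make the text safe, because the instruction to censor is explicit and unqualified.

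A reader might infer more than the documents support:
- **That a switcher who dies at 8 weeks is lost from every analysis.** That fits iRECIST PFS. For PFS by PCWG3 and for PFS2, PSA would normally have been taken at about weeks 3 and 6. If PSA counts, the rule would not apply.
- **That PFS2 patients leave on day 1.** They are censored at the switch.
- **That main PFS is materially biased.** The mITT set already leaves out most patients whom the rule could touch.
- **That the larger percentages are the expected ones.** The only survival figure in the documents is a median of 16 to 34 months for mCRPC in general. Patients who have just progressed may do worse, but neither document gives a figure for them.

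The consequence is also limited. Enrollment to Arms 1A and 1B stopped after the interim analysis, OS in the same set counts deaths up to trial discontinuation whether or not there was an assessment, and deaths and individual PFS and PFS2 times are listed.

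**Conclusion.** The contradiction is real. In SAP 8.7.4.1 and 8.7.4.2, as in Protocol 9.4.4, a censoring sentence with no condition on being alive conflicts with an endpoint that counts any-cause death. Followed literally, it turns deaths before the first assessment into non-events and raises the curves.

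Cemiplimab-phase iRECIST PFS is the most exposed: about 6% to 12% of switchers at the protocol's general median survival, and 16% to 29% at assumed medians of 12 to 6 months. For PFS by PCWG3 and PFS2 the share is about 3% to 8% at assumed medians of 16 to 6 months if per-cycle PSA counts, a point the SAP leaves open. Main PFS is affected mainly in the optional ITT analysis. These sizes rest on exponential survival and show scale only; the direction does not depend on them.

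Every endpoint concerned is exploratory. The primary ORR and the Simon two-stage design do not use PFS and are unaffected.

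**What to change.** In SAP 8.7.4.1 (PFS) and 8.7.4.2 (PFS and PFS2):
- Apply the no-assessment rule only to patients with no post-baseline response assessment who have not died. Count a death on or before trial discontinuation as an event on its date, which keeps the SAP's existing limit on deaths.
- State whether a PSA result counts as a response assessment for PFS by PCWG3 and for PFS2.
- Record the departure from Protocol 9.4.4 in SAP 13.1. The protocol leaves additional censoring rules to the SAP.

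Two corrections belong in the same edit. The general censoring rule for PFS2 refers to patients with no progression since first IMP, but everyone in that set has already progressed; it should refer to progression since the start of cemiplimab. The censoring formulas for cemiplimab-phase PFS and PFS2 divide by 30.375, whereas SAP 8.2 defines a month as 30.4375 days. The error is about 0.2%, but the formulas should agree.

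The cost is one sentence in three places, a line on PSA, an entry in SAP 13.1 and the two small corrections. No new data are needed. Reported PFS and PFS2 may become slightly less favourable.

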8.7.5 Further efficacy analyses

Survival status and biochemical recurrence

Survival status will be assessed at month 6 and month 12, beginning from the day of the last IMP dose and continues until the patient dies or withdrawal from the trial.

Disease status (CR, PR, SD, PD, Unknown) will be collected for all patients in Part 1 and Part 2 on the survival follow-up CRF page and will be summarized with absolute and relative frequencies at time points as collected during the survival follow-up reporting period.

Biochemical recurrence after radical prostatectomy based on the post-treatment PSA levels at Efficacy FU Month 6 and FU Month 12 will be summarized for patients in Arms 2 and 3.

For LPC patients (Arm 2 and Arm 3) the time (in days) from treatment start to post treatment prostatectomy will be reported.

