The sponsor's ongoing Lipo-MERIT Phase 1 clinical trial in melanoma (NCT02410733) has provided promising signals for single agent and anti-PD-1 combination activity of RNA-LPX cancer vaccine against melanoma-shared antigens in pretreated checkpoint inhibitor-experienced patients with high medical need and limited treatment options. It has further demonstrated that in almost every patient the vaccine executes its MoA, inducing T cells against at least one of the antigens. A considerable fraction of these immune responses was strong (measurable *ex vivo*) and both new T cells were primed and pre-existing T cells were expanded. Responses were both CD8+, but also CD4+, indicating that effector T cells received cognate T cell help in the priming process. It is expected that, in particular for patients that are refractory to anti-PD-1 (meaning that activation of pre-existing memory T cells only is not sufficient to mediate clinical activity), combining the vaccine with anti-PD-1 (which would rescue newly primed T cells specificities from exhaustion) is synergistic. This expectation is supported by data from non-clinical experiments.

Arm 1A and Arm 2 of the proposed clinical trial explores a combination of BNT112 and cemiplimab, anti-PD-1 antibody. Antibodies to PD-1/PDL-1 have been shown to be effective therapeutic options for cancer treatment. Cemiplimab is a fully human monoclonal antibody against PD-1 and is currently being evaluated in patients with advanced solid malignancies and B-cell lymphomas whose cancer are incurable and/or have failed to respond to or showed tumor progression despite standard therapy, or patients who are not candidates for standard therapy, or for whom no available therapy is expected to convey clinical benefit. Cemiplimab has demonstrated efficacy (based on ORR and DoR) and is approved in the U.S. for patients with advanced CSCC, NSCLC, and BCC. Patients in Arm 1b will be given the option to be treated with cemiplimab monotherapy after progression with BNT112 monotherapy.

In addition to the potential safety risks, there is a potential unknown risk related to a delayed radical prostatectomy in patients with newly diagnosed LPC. In order to address this risk, patients will be followed for up to 12 months after the last dose of either IMP and the treating physicians will be able to adjust the treatment also during the course of the trial in case earlier intervention is needed.

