5 INTERIM ANALYSES AND ANALYSIS SEQUENCE

The interim analysis was performed based on all available data from the clinical data cut-off that will occur when the required number of patients in the respective arm had performed the first post-baseline tumor assessment or had been diagnosed with unequivocal clinical progression.

The final analysis of the trial will be performed based on all available data from a clinical data cut-off that will occur after patients in the respective setting of Part 2 (Arms 1A, 1B, and 2, 3) have completed 8 cycles of treatment or discontinued.

However, after the interim analysis, the enrollment of Part 2 Arms 1A and 1B (mCRPC) was stopped prior to the complete enrollment of the planned LPC patients. Therefore, the final analysis for mCRPC and the final analysis for LPC are planned to be performed separately.

The final analysis for mCRPC will be performed based on all available data from a clinical data cut-off that will occur after all the enrolled patients in Part 2 Arms 1A and 1B (mCRPC) have completed 8 cycles of treatment or discontinued.

The final analysis for patients with LPC will be performed based on all available data from a clinical data cut-off that will occur after all the planned patients in the Part 2 Arms 2 and 3 (LPC) have completed 8 cycles of treatment or discontinued.

Note: for both final analyses, the data from both LPC and mCRPC will be analyzed.

- At the final analysis for mCRPC, all the data for LPC up to the data cutoff for this analysis will also be analyzed.
- At the final analysis for LPC, all the data for mCRPC up to the data cutoff for this analysis will also be analyzed.

A further analysis, termed Follow-up analysis, will be performed when the last patient discontinues from the trial. For the Follow-up analysis only a subset of TFLs generated for the main analysis may be produced again, this analysis will include all new data collected in the database. All TFLs to be generated for the Follow-up analysis will be defined after the final analysis has been performed.

An Independent Data Monitoring Committee is not planned for this trial.

The patient's safety will be monitored throughout the trial by the SRC. The SRC will be chaired by the sponsor's Medical Monitor and membership will include at a minimum the trial principal investigators, members of the sponsor medical and safety departments, as well as additional staff as appropriate.

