8 STATISTICAL ANALYSES

8.1 General considerations

In general, the statistical analysis will be performed by trial part (i.e., Part 1 and Part 2) and by treatment group in the Part 2 (i.e., Part 1 mCRPC W_pro1, Part 2 mCRPC W_pro1 + Cemiplimab, Part 2 mCRPC W_pro1, Part 2 LPC W_pro1 + Cemiplimab, Part 2 LPC W_pro1). A detailed description of treatment labels to be used for the analysis is provided in Section 13.4.

For Part 2 of the trial all analyses (disposition, baseline characteristics, efficacy and safety (except adverse event (AE) analysis)) will be analyzed by treatment group and in addition for 3 combined treatment groups “Part 2 Total mCRPC”, “Part 2 Total LPC” and “Part 2 Total”. “Part 2 Total” is an optional treatment group only for some predefined tables.

AE analyses will be analyzed for 6 additional combined treatment groups i.e. “Part 2 Total Monotherapy”, “Part 2 Total Combination Therapy”, “Part 2 Total”, “Parts 1 and 2 Total mCRPC”, “Parts 1 and 2 Total Monotherapy” and “Parts 1 and 2 Total”. A detailed description of all combined treatment groups is available in Section 13.4.

Continuous variables will be summarized by treatment group using the following descriptive statistics: number of patients with non-missing data (n), mean, standard deviation, median, minimum, maximum, lower quartile (Q1) and upper quartile (Q3) where appropriate.

Categorical variables will be summarized by treatment group presenting absolute and relative frequencies (n and %) of patients in each category.

Shift tables from baseline will summarize only cases, where both time points are available, to avoid a “missing” category. The percentages are calculated with respect to the available patients.

Generally, only measurements at scheduled visits will be summarized and included in the tables by visit. Unscheduled measurements will be included in the listings, only.

Time-to-event-endpoints (DoR, PFS, and OS) will be analyzed using Kaplan-Meier methodology and censored in accordance with the US FDA Guidance: “Clinical Trial Endpoints for the Approval of Cancer Drugs and Biologics” [6].

The median survival time (including two-sided 95% confidence limits according to Brookmeyer and Crowley) and the first and third quartiles will be presented for each treatment group. Survival rates (including 95% confidence interval (CI) based on Greenwood's formula) as well as the number and percentage of patients with events,

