Time from treatment start to post treatment prostatectomy for LPC patients (in days):

For date of prostatectomy or radical prostatectomy, missing day will be replaced with the first day of the month. In case month is not reported, missing month will be replaced with July.

Time from treatment start to prostatectomy (days) will be calculated as:

(Date of prostatectomy – date of first IMP administration (W_pro1 or cemiplimab) + 1

Study day:

Study day is defined as follows:

If date of assessment is on or after the date of first IMP administration (W_pro1 or cemiplimab):

- Date of assessment – date of first IMP administration + 1

If date of assessment is before date of first IMP administration (W_pro1 or cemiplimab):

- Date of assessment – date of first IMP administration

Laboratory values with “< xx” or “> xx”:

Any laboratory values given as “< xx” or “> xx” in the database will be imputed with the numeric value of xx without the sign for the descriptive statistics and the calculation of changes from baseline (e.g., a value of < 1 will be imputed as 1 for the calculations).

Last date known to be alive:

Last date known to be alive is defined as last documented date in the database for the patient, including all visit dates, assessment dates (if different from visit dates), trial treatment administration dates, tumor assessment dates, end of treatment dates, date of trial completion or early trial withdrawal date, start/stop dates of AEs, PSA response date, survival follow-up date (where patients survival status is alive), whichever comes last.

Start of Follow-up Period:

Part 1 and Part 2 mCRPC patients: Follow-up period starts at the administration of the last dose of IMP.

Part 2 LPC patients: Follow-up period starts at the last administration of IMP at Cycle 8 or at administration of the last IMP in case of discontinuation of trial treatment.

Pooling of centers:

No pooling of centers is planned for this trial.

Conventions for imputing missing/partially missing dates:

When computations on dates are to be performed, incomplete/missing dates will be imputed using the following rules.

- Missing day, month/year present: If the month/year is the same as the month/year of the first IMP administration date, then impute missing start dates with first IMP administration date. Otherwise, for dates corresponding to a start date, impute with the first day of the month and, for dates corresponding to a stop date, impute with the last day of the month.

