8.3 Missing Data

All reasonable efforts will be made to obtain complete data for all patients. However, missing observations may occur due to patients lost to follow-up or to noncompliance with required trial visits and / or assessments. Missing data will not be imputed and data analysis will be performed based on the observed values, unless otherwise specified.

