	14.2.4.1.7a	Progression-free Survival (PFS) based on PCWG3, SAS output	Cemi Mono on PD set	
Figure	14.2.4.1.8	Kaplan-Meier curve for Progression-free Survival (PFS) based on PCWG3	Cemi Mono on PD set	
	14.2.4.1.9	Progression-free Survival (PFS) based on iRECIST (central reading)	Cemi Mono on PD set	
	14.2.4.1.9a	Progression-free Survival (PFS) based on iRECIST (central reading), SAS output	Cemi Mono on PD set	
Figure	14.2.4.1.10	Kaplan-Meier curve for Progression-free Survival (PFS) based on iRECIST (central reading)	Cemi Mono on PD set	
	14.2.4.1.11	Progression-free Survival 2 (PFS2) based on PCWG3	Cemi Mono on PD set	
	14.2.4.1.11a	Progression-free Survival 2 (PFS2) based on PCWG3, SAS output	Cemi Mono on PD set	
Figure	14.2.4.1.12	Kaplan-Meier curve for Progression-free Survival 2 (PFS2) based on PCWG3	Cemi Mono on PD set	
	14.2.4.1.13	Overall Survival (OS)	Cemi Mono on PD set	
	14.2.4.1.13a	Overall Survival (OS) SAS output	Cemi Mono on PD set	
Figure	14.2.4.1.14	Kaplan-Meier curve for Overall Survival (OS)	Cemi Mono on PD set	
14.2.5		Further Efficacy Analyses		
	14.2.5.1.1	Disease status during Survival Follow-up Period	mITT set	
	14.2.5.1.2	Biochemical recurrence after radical prostatectomy – post-treatment PSA values	mITT set	
	14.2.5.1.3	Time from treatment start to post-treatment prostatectomy – LPC patients	mITT set	
14.3		Safety Data		
14.3.1		Displays of Adverse Events		
	14.3.1.1	Summary of adverse events	Safety set	Yes
	14.3.1.2	Number (%) of patients with TEAEs by system organ class and preferred term	Safety set	Yes
	14.3.1.3	Number (%) of patients with TEAEs related to IMP by system organ class and preferred term	Safety set	Yes
	14.3.1.4	Number (%) of patients with TEAEs related to W_pro1 by system organ class and preferred term	Safety set	

Header	Table Number	Name	Analysis Set	Interim Analysis
	14.3.1.5	Number (%) of patients with TEAEs related to Cemiplimab by system organ class and preferred term	Safety set	
	14.3.1.6	Number (%) of patients with maximum intensity grade ≥ 3 TEAEs by system organ class and preferred term	Safety set	Yes
	14.3.1.7	Number (%) of patients with maximum intensity grade ≥ 3 TEAEs related to IMP by system organ class and preferred term	Safety set	Yes
	14.3.1.8	Number (%) of patients with maximum intensity grade ≥ 3 TEAEs related to W_pro1 by system organ class and preferred term	Safety set	Yes

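### Days to prostatectomy in the LPC arms are summarised only for patients with a surgery date and without censoring, so the summary leans toward short times for a risk the protocol names

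*SAP*

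**What the plan says.** Protocol section 2.3 states that "there is a potential unknown risk related to a delayed radical prostatectomy in patients with newly diagnosed LPC". Section 2.2 relies on the added treatment not delaying the planned surgery as part of the case for this setting.

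The SAP's measure is in section 8.7.5: "For LPC patients (Arm 2 and Arm 3) the time (in days) from treatment start to post treatment prostatectomy will be reported". Section 8.2 derives it as "Date of prostatectomy – date of first IMP administration (W_pro1 or cemiplimab) + 1". The only missing-date rule attached to it completes a partial surgery date; nothing is said about a patient with no surgery. The output is Table 14.2.5.1.3, "Time from treatment start to post-treatment prostatectomy – LPC patients", in the mITT set, with no accompanying curve.

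Three general rules govern how the table will be filled:

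- SAP 8.1: "Time-to-event-endpoints (DoR, PFS, and OS) will be analyzed using Kaplan-Meier methodology". Time to prostatectomy is not in that list.
- SAP 8.3: "Missing data will not be imputed and data analysis will be performed based on the observed values, unless otherwise specified".
- SAP 8.1 has continuous variables summarised by "number of patients with non-missing data (n), mean, standard deviation, median" and further statistics; SAP 10.2.4 puts the analysis-set size N in the column header.

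On timing, SAP section 5 sets the LPC final cut-off "after all the planned patients in the Part 2 Arms 2 and 3 (LPC) have completed 8 cycles of treatment or discontinued". Protocol 8.3.3 puts surgery after the EoT visit. SAP section 5 also analyses LPC data at the mCRPC cut-off, and plans a Follow-up analysis after the last patient leaves the trial, for which only a subset of outputs, chosen later, may be rerun.

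**The concern.** Time to surgery is a time-to-event variable, but the plan treats it as a simple continuous one. At any cut-off, the patients without a value are those who have not reached surgery: recent enrollees, those delayed, those cancelled. A given patient is more likely to be missing the longer his interval is, so the observed-only mean and quantiles are right-truncated and lean short.

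The cut-off adds to this. It waits for the last patient's eighth cycle, not for his operation, so patients finishing near the end can still be awaiting surgery. A cancelled operation never gets a value at any cut-off.

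This table is the SAP's only direct summary of a risk the protocol chose to name. With about 20 patients per arm, a few men unoperated or operated late would be the signal, and the days summary is least able to show them.

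**Working it through.** **Step 1: the plan's own timing.** Cycles last 21 days. Cycle 8 starts after (8 − 1) × 21 / 7 = 21 weeks, which matches protocol 8.3.3. Cycle 8 ends at 8 × 21 = 168 days. The earliest LPC final cut-off, with no early discontinuation, is therefore 168 days after the last patient's first dose.

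**Step 2: what is missing.** The documents give no accrual period for the LPC arms, no interval from EoT to surgery, and no delay or cancellation rate. These are assumed below. N = 40 (20 per arm) comes from SAP section 6.

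**Step 3: first model.** Uniform accrual over 6 to 24 months; cut-off at last entry + 168 days; surgery at day 168 plus a gamma-distributed gap (shape 4) with mean 2, 4 or 8 weeks. Variant (a) has no extra delay or cancellation. Variant (b) has 10% cancelled and 15% delayed by a further 12 weeks. Averages over 4,000 simulated trials; medians in days:

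| Accrual, gap, variant | With a date | Pending | Cancelled | Median, dated only | Median, all eventually operated | Kaplan-Meier median |
|---|---|---|---|---|---|---|
| 24 mo, 2 wk, (a) | 38.2 | 1.8 | 0 | 180.9 | 180.9 | 181.0 |
| 12 mo, 4 wk, (a) | 36.0 | 4.1 | 0 | 193.3 | 193.8 | 193.9 |
| 12 mo, 4 wk, (b) | 31.1 | 4.9 | 4.0 | 195.6 | 197.0 | 199.9 |
| 6 mo, 8 wk, (a) | 26.7 | 13.3 | 0 | 214.3 | 219.7 | 219.8 |
| 6 mo, 8 wk, (b) | 21.6 | 14.4 | 4.0 | 216.2 | 226.3 | 232.6 |

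Pending runs from 1.8/40 = 4% to 14.4/40 = 36%. The shortfall of the dated-only median against Kaplan-Meier runs from 0.1 to 232.6 − 216.2 = 16.4 days. In that worst row, 226.3 − 216.2 = 10.1 days come from truncation. The other 232.6 − 226.3 = 6.3 days arise because Kaplan-Meier here keeps cancelled patients unoperated.

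For the share more than 8 weeks past the end of Cycle 8, take 12 months, 4 weeks, variant (b). It is 15% among patients with a date, against 27% late or never operated among all 40. Part of that gap is definitional. Taking out the 10% cancelled gives (0.27 − 0.10)/0.90 = 19% late among those eventually operated on. So 15% against 19% reflects truncation, and the rest is cancelled surgery that a days summary cannot carry.

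**Step 4: second model, with a long tail.** Entry uniform over A days; surgery at day 169 + U(14, 42), plus, in a fraction of patients, an exponential extra delay; same cut-off; late means after day 225. The true mean can be checked by hand: 169 + 28 + 0.20 × 180 = 233, and with 30% delayed, 169 + 28 + 0.30 × 180 = 251.

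| A, delayed, mean extra delay | Operated at cut-off | Mean: dated / true | Median: dated / true | Late: dated / true |
|---|---|---|---|---|
| 365, 20%, 180 d | 81% | 207 / 233 | 199 / 200 | 9% / 17% |
| 730, 20%, 180 d | 89% | 216 / 233 | 199 / 200 | 13% / 17% |
| 365, 30%, 180 d | 77% | 212 / 251 | 200 / 203 | 14% / 26% |
| 365, 20%, 60 d | 86% | 205 / 209 | 199 / 200 | 10% / 13% |
| 365, none | 90% | 197 / 197 | 197 / 197 | 0% / 0% |
| 365, 20%, 180 d, cut-off 60 d later | 92% | 209 / 233 | 199 / 200 | 10% / 17% |

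The direction holds throughout: dated-only values are at or below the true ones. The table is nearly right when nobody is delayed and understates the mean and late share when some are.

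**The case against.** A reader might infer four stronger things, and the other side is right on each.

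- *Many surgeries fall after the cut-off.* Not supported. The cut-off comes after all planned LPC patients finish 8 cycles or discontinue, so earlier patients have usually had time for surgery, and protocol 7.1 allows surgery during treatment. The second model has 77% to 90% operated on at the earliest possible cut-off. The defensible statement is some, mainly the last enrolled. The share may be larger in the LPC tables run at the mCRPC cut-off.
- *Unoperated patients vanish.* Not quite. N and n are both displayed, so N minus n can be read by arm. It does not separate pending, cancelled and withdrawn. The mock tables are a separate document and might add a row; the SAP text does not call for one.
- *Nothing else captures surgery.* SAP 8.6.5 tabulates procedures, including surgery, up to the Safety FU-D30 or FU-D90 visit, which may pick up some prostatectomies. It gives no time to surgery, and longer delays fall outside the window.
- *Late surgeries are lost for good.* The Follow-up analysis will hold all later data. What is missing is a commitment to rerun this table, and cancelled operations would still have no value.

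The size also rests on assumed delays. The median moves by only a few days in most settings, and a mean extra delay of 60 days instead of 180 cuts the bias in the mean to about 2 to 4 days. A later cut-off raises the operated share but does not cure the tail: 60 days more gives 92% operated, with a mean of 209 against 233.

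The mITT point is minor: a clinical assessment also qualifies, and imaging before surgery is required. Finally, time to surgery is not an endpoint in protocol Table 3-1, both LPC arms receive BNT112, and no reference interval is given. No analysis here can show delay relative to usual timing; it can only describe the interval without bias.

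**Conclusion.** The point stands as a modest, well-founded improvement. As written, the SAP summarises a right-truncated, operated-only subset for a risk the protocol names, and it states neither a censoring rule nor an operated/not-operated count. Confidence is high on structure and direction.

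The size cannot be fixed from the documents. Over accrual of 6 to 24 months and mean surgery gaps of 2 to 8 weeks, about 4% to 36% of patients are pending and the median is low by about 0 to 16 days, with the upper end needing fast accrual, a long gap and some cancellations. With 20% to 30% of patients facing a mean extra delay of 180 days, the mean is low by 17 to 39 days (233 − 216; 251 − 212), and a true late share of 17% to 26% reads as 9% to 14%. Without such a tail the distortion is small. The documents do not support a claim that most of the delay signal is lost.

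**What to change.** In SAP 8.7.5 and Table 14.2.5.1.3, for all treated LPC patients and by arm:

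1. Report the number and percentage operated on and not operated on by the cut-off, separating pending from definitively cancelled where the collected data allow.
2. Estimate time from first dose to prostatectomy by Kaplan-Meier or cumulative incidence. Censor unoperated patients at last contact, and treat death and documented cancellation as competing events; simple censoring at cancellation would assume those patients could still be operated on later.
3. Commit to repeating the table at the Follow-up analysis.

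The cost is SAP wording, one revised table and slightly more analysis work. The surgery date is already collected (protocol 8.3.3), and surgical procedures after stopping IMP are recorded to Month 12 (protocol 1.4, footnote 7). Cancellation and its reason may not be fully captured on the eCRF, so it should not be promised that no new data are needed. With about 20 patients per arm the curves will be imprecise, and the counts will carry most of the information. No change to the timing or management of surgery is proposed.
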